# 8.6. Off study criteria

*Per subject choice:* Subjects may withdraw from study at their request. The risks of withdrawing will be discussed, as will alternative treatment options. Those subjects who choose to withdraw while taking eltrombopag will be strongly encouraged to continue to have labs monitored until he/she initiates alternative therapy.

**Per principal investigator decision:** Should any of the following events occur during the study period, or in the extension treatment arm in responders, EPAG will be discontinued. The subject will be followed until resolution of the event. For study purposes labs relevant to the adverse event will be monitored for 30 days after discontinuation of EPAG. We will offer patients a follow-up evaluation at the NIH 6 months following being taken off EPAG treatment either due to lack of response or because they met other criteria for coming off study, but this visit will not be required. If they do not return to the NIH, we will contact their primary hematologist for information on their current hematologic status 6 months following their final dose of eltrombopag, and then take

them off study. If a patient initiates an alternative disease directed therapy at any time, the subject's participation on this study will be considered complete and the subject will go off study.

- Intolerance of EPAG not resolved by dose reduction
- Life threatening acute hypersensitivity reaction
- Thrombosis/embolism (DVT, PE, stroke or TIA, myocardial infarction) other than central line thrombosis
- Persistent hepatotoxicity as defined in §10.3.1
- New or worsening morphological abnormalities or cytopenia(s) indicative for transformation to MDS or AML
- No treatment response by week 24 (+/- 7 days)
- Any Grade IV toxicity considered related to the study medication excluding readily reversible metabolic or laboratory abnormalities or hematologic toxicities (see §9.2.1, 10.3.1)
- Significant progression of disease such as development of a solid tumor while on EPAG, or a concomitant condition that would make the subject ineligible for further protocol participation
- Pregnancy or unwillingness to use acceptable forms of contraception
- Initiation of non-protocol therapy for Diamond-Blackfan anemia
- Subject non-compliance
- Lost to follow-up

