Adverse Events that meet the criteria of CTCAE v 5.0 grade 2 and above plus laboratory abnormalities that meet the definition of an AE will be captured at each study visit on the appropriate case report form (CRF) regardless of relationship. AEs and SAEs whether volunteered by the patient, discovered by study personnel during questioning, or detected through physical examination, clinically significant laboratory test, or other means will be recorded. Information to be collected includes event description, time of onset, clinician's assessment of severity, relationship to study drug and study procedure (assessed only by those with the training and authority to make a diagnosis), and time of resolution/stabilization of the event. These AEs will be followed to adequate resolution.

Abnormal non-hematologic laboratory values recorded in the database will be recorded at the highest grade and resolved in the database when the value is a grade 2 or lower. However, with the exception of ALT, AST and direct bilirubin any laboratory abnormalities higher than grade 2 will automatically result in discontinuation of the study drug.

Hypertension CTCAE v5 Grade 1 is not an applicable category for this study and therefore only hypertension greater than grade 2, that require medical intervention, will be documented.

Unscheduled laboratory results or patient reports that have been sent in addition to the protocol required ones will be reviewed for AEs and will be recorded on secure network drives or in approved alternative sites that comply with NIH information security standards and not in the research database.

Thirty days after the last dose of study drug, adverse event collecting and reporting will be limited to serious adverse events considered possibly, probably, or definitely related to study drug.

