# Hepatotoxicity

PROMACTA may increase the risk of severe and potentially life-threatening hepatotoxicity. Measure serum ALT, AST, and bilirubin prior to initiation of PROMACTA, every 2 weeks during the dose adjustment phase, and monthly following establishment of a stable dose. PROMACTA inhibits UDP-glucuronosyltransferase-1A1 (UGT1A1) and organic anion-transporting polypeptide-1B1 (OATP1B1), which may lead to indirect hyperbilirubinemia. If bilirubin is elevated, perform fractionation. Evaluate abnormal serum liver tests with repeat testing within 3 to 5 days. If the abnormalities are confirmed, monitor serum liver tests weekly until resolved or stabilized. Discontinue PROMACTA if ALT levels increase to greater than or equal to 3 x ULN in patients with normal liver function or greater than or equal to 3 x baseline (or greater than 5 x ULN, whichever is the lower) in patients with pre-treatment elevations in transaminases and are:

- progressively increasing, or
- persistent for greater than or equal to 4 weeks, or
- accompanied by increased direct bilirubin, or
- accompanied by clinical symptoms of liver injury or evidence for hepatic decompensation.

If the potential benefit for reinitiating treatment with PROMACTA is considered to outweigh the risk for hepatotoxicity, then consider cautiously reintroducing PROMACTA and measure serum liver tests weekly during the dose adjustment phase. Hepatotoxicity may reoccur if PROMACTA is reinitiated. If liver test abnormalities persist, worsen, or recur, then permanently discontinue PROMACTA.

Isolated cases of severe liver injury were identified in clinical trials. The elevation of liver laboratory values occurred approximately three months after initiation of PROMACTA. In all cases, the event resolved following PROMACTA discontinuation.

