# Investigator Brochure, Version 13, dated 4/13/2016 - "Adverse Events considered to be Expected for Reporting Purposes"

Below are lists of "Adverse Events considered to be Expected for Reporting Purposes" for each chronic ITP and SAA. This list is based upon evaluation of the available clinical safety information, including data from all global clinical trials (phase I-III) and the Novartis safety database, Argus (cut-off date of 29 February 2016).

Adverse reactions are listed below for each indication by MedDRA body system organ class and by frequency. Frequency category for each adverse drug reaction is based on the following convention (CIOMS III). The frequency categories used are:

- Very common: ≥1 in 10 (≥10%)
- Common: ≥1 in 100 and <1 in 10 (≥1% and <10%)
- Uncommon: ≥1 in 1,000 and <1 in 100 (≥0.1% and <1%)
- Rare: ≥1 in 10,000 and <1 in 1,000 (≥0.01% and <0.1%)

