# Table 10: Adverse events considered to be expected for reporting purposes in chronic ITPadults

Infections and infestations				
Common:	Pharyngitis			
	Urinary tract infection			
Gastrointestinal di	Gastrointestinal disorders			
Very Common:	Nausea			
	Diarrhea			
Common:	Dry mouth			
	Vomiting			
Hepatobiliary diso	rders			
Common:	Increased aspartate aminotransferase			
	Increased alanine aminotransferase			
	Blood bilirubin unconjugated increased			
Uncommon:	Drug-induced liver injury			
Skin and subcutane	eous tissue disorders			
Common:	Alopecia			
	Rash			
Musculoskeletal and connective tissue disorders				
Common:	Back pain			
	Musculoskeletal chest pain			
	Musculoskeletal pain			
	Myalgia			
Vascular disorders				
Rare: post-marketin	g cases of Thrombotic microangiopathy with acute renal failure reported			
spontaneously				

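### The automatic laboratory stop in 9.2.2 exempts direct but not total bilirubin, so whether an isolated indirect rise stops drug depends on which assay the laboratory ran

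*Combined protocol and SAP*

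**What the plan says.** **The stop.** Section 9.2.2, in its paragraph on non-hematologic laboratory values, states that "with the exception of ALT, AST and direct bilirubin any laboratory abnormalities higher than grade 2 will automatically result in discontinuation" of study drug. The sentence sets no condition on attribution, reversibility or bilirubin fraction.

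**The assay.** Sections 6.3, 6.5 and 6.5.1 and Tables 14 and 15 accept either total or direct bilirubin at the interim draws, alongside ALT and AST. Both are required at the 3- and 6-month landmarks (6.4) and every 6 months in the extension. Interim testing may be done by the home physician.

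**The liver guidance.** Section 10.3.1 says the drug inhibits UGT1A1 and OATP1B1, "which may lead to indirect hyperbilirubinemia", and adds: "If bilirubin is elevated, perform fractionation". Its discontinuation criteria need a raised ALT plus one further feature; the only bilirubin feature among these is an increase in the direct fraction. Table 10 lists "Blood bilirubin unconjugated increased" as common in adult ITP. The entry limit in 4.2.3 is also set on direct bilirubin. Table 4 covers isolated ALT or AST elevation only.

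**The off-study list.** Section 8.6 discontinues drug for "Any Grade IV toxicity considered related to the study medication excluding readily reversible metabolic or laboratory abnormalities or hematologic toxicities" and for "Persistent hepatotoxicity as defined in §10.3.1". The automatic stop of 9.2.2 does not appear there.

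**The concern.** A discontinuation rule should give the same answer for the same patient. Here two subjects with the same isolated indirect rise can be handled differently because their local laboratories reported different assays. The exemption also fails on its own terms: total contains direct, so exempting direct has little effect whenever total is measured.

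At stake is a subject's exposure to drug before the 24-week assessment, for a finding that 10.3.1 alone would not treat as a reason to stop. The size of that loss is unclear because 9.2.2 does not say whether the stop is permanent, and Table 2 uses the same verb for a one-week hold. If the stop is a hold, 5.1 gives make-up time only when the interruption is not due to a severe drug-related adverse event. Table 7 labels grade 3 as severe, so a drug-related grade 3 rise may not qualify.

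**Working it through.** **1. How often the assay choice is open.** From Table 14, either assay is accepted at weeks 2, 4, 6, 8, 10, 14, 16, 18, 20 and 22, which is 10 draws. The full panel is taken at week 12 and month 6, which is 2. So 10/12 draws leave the choice open. In a full 3-year extension on drug there are 36 monthly draws, of which 6 coincide with six-monthly full panels: 36 − 6 = 30, so 30/36. These counts show what is permitted, not how often direct is run alone. Full panels are at most about 12 weeks apart in the first 6 months and about 6 months apart in the extension, which bounds how long a rise could go unseen.

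**2. The same rise under each assay.** Total = direct + indirect. Take a subject with normal direct bilirubin, ALT below the 10.3.1 threshold, and an indirect rise that puts total above grade 2.

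| Assay run | Result seen | Action under 9.2.2 |
|---|---|---|
| Total only | Total above grade 2 | Automatic stop |
| Direct only | Normal | None until the next full panel |
| Both | Total above grade 2, direct normal | Automatic stop; no text lifts it |

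Fractionation under 10.3.1 would identify the rise as indirect, but 9.2.2 makes no exception once that is known. With direct alone, nothing prompts fractionation.

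**3. Against 8.6.** The toxicity item in 8.6 requires grade IV, relatedness, and something other than a readily reversible laboratory abnormality. Section 9.2.2 acts from grade 3 with none of these conditions. For a non-exempt test, a readily reversible grade IV value is spared by that item in 8.6 but has already stopped drug under 9.2.2. The exclusion therefore has no work to do for those tests. This applies to every test that 9.2.2 covers, not only bilirubin.

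**4. Possible frequency.** The documents give no rate of isolated indirect bilirubin above grade 2. The nearest figure is an assumed proxy: in the long-term ITP extension study described in 2.4.6, 4 of 302 patients withdrew for increased bilirubin (fraction and grade not stated), at a median average daily dose of 50.4 mg and a median exposure of 2.4 years.

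- Rate: 4/302 = 1.32% (Clopper-Pearson 95% CI 0.36 to 3.36%).
- Unscaled, in case liver effects come early: expected cases in 25 = 25 × 0.0132 = 0.33 (0.09 to 0.84). P(at least one) = 1 − (1 − p)^25 = 28% (9 to 57%). P(zero or one) = (1 − p)^25 + 25p(1 − p)^24 = 96%, or 80% at the upper limit.
- Scaled to 24 weeks under constant hazard: 0.46/2.4 = 0.192; 1.32% × 0.192 = 0.25% (0.07 to 0.64%). Expected = 0.06; P(at least one) = 6% (2 to 15%).

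The common category behind Table 10 runs from 1% to below 10%, so 25 × 0.01 = 0.25 to just under 25 × 0.10 = 2.5 cases of any grade; the share above grade 2 is not given. In the severe aplastic anemia trial, at up to 150 mg, 2.4.3 reports escalation without dose-limiting toxicities and Table 9 does not list bilirubin. Absence from an adverse-reaction table is not a count of laboratory values.

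**5. Power, for scale only.** Power of the 8.3 design is the sum over x = 2 to 15 of P(X1 = x) × P(X2 ≥ 6 − x), with X1 from 15 subjects and X2 from 10. At a response rate of 10% this gives an alpha of 0.033; at 30% it gives a power of 0.802, which agrees with the plan. If 5% of would-be responders were stopped and counted as non-responders, the rate would be 0.30 × 0.95 = 0.285 and power 0.754. The documents give no basis for 5%.

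**The case against.** **The two rules do not contradict each other.** A reader might infer that 9.2.2 and 8.6 conflict outright. They do not: 8.6 is not stated to be exhaustive, its reversibility exclusion limits one item rather than giving a right to stay on drug, and both sections are obeyed by applying the stricter one. This stands. What remains is that the stricter rule empties the exclusion and the two sections do not refer to each other.

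**The two halves weaken each other.** If an isolated indirect rise is not hepatotoxicity, missing it does little harm; and stopping drug when in doubt is defensible for a drug with a boxed hepatotoxicity warning, in a trial that enrols from age 2. This largely stands, and it limits the point to uneven handling in a single-arm pilot. It does not justify letting the choice of assay decide.

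**Safeguards exist.** A reader might infer that liver injury could be missed. On the natural reading of the schedule, ALT and AST are taken at every interim draw, and full panels recur. The documents do not support that inference, nor do they show that any laboratory would run direct bilirubin alone.

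**The trigger cannot be sized.** The grading cut-offs for bilirubin are not reproduced, and the ITP withdrawals may have been direct or mixed rises at a lower dose. This stands: the proxy shows an order of magnitude and no more.

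**Conclusion.** The point holds as a minor defect. The rule as written handles an isolated indirect rise above grade 2 differently according to the assay, and its direct-bilirubin exemption does little once total is measured. Most likely zero or one of 25 subjects is affected. That judgement rests on an ITP proxy at a lower dose with fraction and grade unstated; the documents give no dose-response for bilirubin, so no adjustment was made.

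A reader might also infer a loss of power for the primary endpoint. The documents do not support this: they do not show how many would-be responders the rule would stop, or whether a stopped subject would lose response status at 6 months. The 5% calculation above is an illustration and should not raise the severity.

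**What to change.** 1. In 6.3, 6.5, 6.5.1 and Tables 14 and 15, require total *and* direct bilirubin in place of total *or* direct.
2. Amend 9.2.2 so that a total bilirubin above grade 2 is fractionated before the automatic stop is applied. An isolated indirect rise, with normal direct bilirubin and ALT below the 10.3.1 threshold, should not trigger automatic discontinuation. The investigator stays free to hold drug.
3. Cross-refer 9.2.2 and 8.6 through one rule that says whether the laboratory stop is a hold or permanent, and whether the exclusion for readily reversible abnormalities applies to it. If it is a hold, say whether the make-up time in 5.1 applies. Copying the 9.2.2 stop into 8.6 without these statements would settle nothing.

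The cost is amendment wording, one extra analyte on a tube already drawn, and a slightly less conservative stop for isolated indirect rises.

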#### 8.2. Endpoints

# 8.2.1. Primary endpoint

Primary efficacy endpoint will be the proportion of drug responders at 6 months. Best response (robust or not) will be noted, regardless of when it is achieved; however, for protocol purposes, primary response will be assessed according to patient status at the time of the 6-month primary endpoint assessment. Time-to-response will also be measured according to the time from eltrombopag initiation to the first time the patient met criteria for response.

*Response* to treatment will be defined by one or more of the following:

- Erythroid response for subjects with a pretreatment hemoglobin less than 9 G/dL will be defined as an increase in hemoglobin by >1.5 G/dL from enrollment baseline, *and/or*
- a reduction in the units of PRBC transfusions by at least 50% during the eight consecutive weeks prior to response assessment compared with the pretreatment transfusion number in the previous 8 weeks.

*Robust response* to treatment will be defined both:

- Stable hemoglobin (two consecutive measurements at least 2 weeks apart) greater than 10 g/dL, *and*
- Transfusion independence for the previous 8 weeks

For sub-analyses, *transient response* to treatment (robust or otherwise) is defined as any response meeting the respective criteria above within the first 6 months that is subsequently lost and not regained prior to the 6-month primary endpoint assessment. While note will be made of such patients, for the purposes of primary response analysis, these patients will be considered *non-responders* along with patients who fail to meet the above response criteria.

Primary safety endpoint will be the toxicity profile assessed at 6 months using CTCAE criteria.

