## 8.5. Stopping rules

The study will be monitored to ensure that the occurrence of a specified set of treatment related serious adverse events (TRSAEs) that occur during the treatment period does not substantially exceed an anticipated rate. The following specified TRSAEs determined to be probably or definitely related to EPAG will be considered for early stopping of the study:

- 1. Death considered to be probably or definitely related to eltrombopag
- 2. Any Grade IV toxicity excluding readily reversible metabolic or laboratory abnormalities
- 3. Grade IV thrombosis/embolism

We anticipate the rate of these specified TRSAEs within the 24-week study period to be 20% or less. Following Geller *et al.* (90), our stopping rule is determined by a Bayesian approach. The stopping boundary for an experiment is reached if the Bayesian posterior probability that the true probability of developing one or more of the specified TRSAE's exceeds this benchmark rate of 20% is at least 90%. We take our prior distribution to be a beta distribution with parameters ( $\alpha$ ,  $\beta$ ) = (1, 4). The parameters are chosen so that the mean  $\alpha / (\alpha + \beta) = 0.2$  as the expected proportion of specified TRSAE's and the sum  $\alpha + \beta = 5$  as the "worth" we place on our prior clinical opinion. This indicates that the relative weight we place on our prior opinion is 5/25=20% of the weight we will place on the results of the new study. Hence when we make decisions about stopping the study, the data from the study will dominate over the prior opinion. All participants will be included in monitoring and evaluation for safety. Table 5 summarizes the threshold numbers for stopping the study.

Number of subjects in the experiment	Stop if the number of subjects who have developed any of the specified TRSAE's reaches:
≤ 5	3
≤ 9	4
≤ 12	5
≤ 16	6
≤ 20	7
≤ 24	8

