9.2.2. Adverse events Management

AEs will be graded by severity utilizing CTCAE version 5.0 (summarized in Table 7) and attributed (unrelated, unlikely, possibly, probably or definitely) to study medication and/or disease (Table 8). The current CTCAE grading criteria can be downloaded from the CTEP homepage at:

https://ctep.cancer.gov/protocolDevelopment/electronic\_applications/ctc.htm.

Grade	Category	Description
1	Mild	Mild; asymptomatic; clinical or diagnostic observations only; intervention not indicated
2	Moderate	Moderate; minimal, local or noninvasive intervention indicated; limiting age-appropriate instrumental ADL 
3	Severe	Severe or medically significant but not immediately life-threatening; hospitalization or prolongation of hospitalization indicated; disabling; limiting self-care ADL 
4	Life threatening	Life-threatening consequences; urgent intervention indicated
5	Death	Death related to AE
1-		

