#### Table 8: Attribution of adverse events

Relationship	Attribution	Description
Unrelated to investigational	Unrelated	The AE is clearly NOT related to the intervention
agent/intervention 	Unlikely	The AE is doubtfully related to the intervention
Related to investigational agent/intervention 	Possibly	The AE may be related to the intervention
	Probably	The AE is likely related to the intervention
	Definitely	The AE is clearly related to the intervention

**NOTE:** AEs listed as 'possibly, probably, or definitely' related to the investigational agent/intervention are considered to have a suspected 'reasonable causal relationship' to the investigational agent/intervention (ICH E2A).

In view of the underlying disease (Diamond-Blackfan anemia), all patients will enter the study with abnormally low blood counts that would meet criteria for grade 2 and more commonly higher toxicity. Also, platelet and red blood cell counts will be impacted by frequent transfusions. Therefore, AEs regarding low hematologic lab values, including thrombocytopenia or platelet-transfusion dependence, anemia or red cell transfusion dependence, neutropenia, lymphopenia, or leukopenia are not evaluable and will not be recorded.

Non-hematologic abnormal laboratory findings used to evaluate the safety of this protocol regimen will include any change from laboratory assessments done prior to first dose of study medication that result in a progression to grade 3 or 4 laboratory toxicity or are characterized by any of the following:

- Results in discontinuation from the study
- Is associated with clinical signs or symptoms
- Requires treatment or any other therapeutic intervention
- Is associated with death or another serious adverse event, including hospitalization
- Is judged by the Investigator to be of significant clinical impact
- If any abnormal laboratory result is considered clinically significant, the investigator will provide details about the action taken with respect to the test drug and about the patient's outcome.

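### Section 9.2.2 sets two conflicting recording thresholds for grade 2 hypertension; read literally, the narrower one understates the hypertension line of the 6-month toxicity profile

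*Combined protocol and SAP*

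**What the plan says.** Section 9.2.2 (Adverse events Management) gives the general rule for the case report form: "Adverse Events that meet the criteria of CTCAE v 5.0 grade 2 and above" are to be captured at each study visit whatever their relationship to study drug, together with laboratory abnormalities that qualify as adverse events.

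Two paragraphs later the same section makes a separate statement for one event. It begins "Hypertension CTCAE v5 Grade 1 is not an applicable category for this study and therefore" and concludes that "only hypertension greater than grade 2, that require medical intervention, will be documented".

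Section 8.2.1 defines what these records feed: "Primary safety endpoint will be the toxicity profile assessed at 6 months using" CTCAE criteria. It states no grade cut-off and no exception for hypertension.

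Section 9.2.2 also contains other event-specific rules. Low blood counts are exempt: "neutropenia, lymphopenia, or leukopenia are not evaluable and will not be recorded" closes that list, and the reason given is that counts are abnormal at entry and affected by transfusion. Non-hematologic laboratory findings have their own criteria, namely progression to grade 3 or 4 or one of several listed consequences. Hypertension falls under neither rule.

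**The concern.** At grade 2 the general rule says to record and the hypertension sentence says not to. The hypertension sentence is the more specific of the two and contains the word *only*, so a data manager could reasonably let it prevail. Its stated reason does not support that outcome. Saying that grade 1 does not apply explains leaving out grade 1; it does not explain leaving out grade 2.

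Safety is half of the primary objective (Sections 1 and 8.1). If the narrower rule is followed, the hypertension row of the toxicity table rests on a different threshold from the other clinical events beside it, and nothing in the plan would tell the reader so. Inconsistent application is also possible. Section 6.3 allows subjects to be followed by home physicians whose notes are sent to the study team, so the rule may be applied to notes from many sources.

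**Working it through.** No figure in the plan depends on this rule, so the check is mainly a comparison of texts.

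**Step 1. What each rule records.** *Greater than grade 2* means grade 3 or higher. The clause about medical intervention can be read as a further filter or as a description of the grade. That gives four readings of the hypertension sentence, set here against the general rule for non-serious events:

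| Rule or reading | Grade 1 | Grade 2 | Grade 3+, intervention | Grade 3+, no intervention |
|---|---|---|---|---|
| General rule | no | yes | yes | yes |
| Literal grade, clause as filter | no | no | yes | no |
| Literal grade, clause as description | no | no | yes | yes |
| Slip for grade 2 or greater, clause as description | no | yes | yes | yes |
| Slip for grade 2 or greater, clause as filter | no | only with intervention | yes | no |

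Only the third of the four hypertension readings agrees with the general rule throughout.

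**Step 2. Does the stated reason select a reading?** It concerns grade 1, and grade 1 is *no* in every row. It therefore gives no support for removing grade 2 or for adding an intervention condition.

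**Step 3. Does the grading table help?** Table 7 describes grade 2 as "Moderate; minimal, local or noninvasive intervention indicated; limiting age-appropriate instrumental ADL". Intervention is thus already part of the grade 2 description, which fits the idea that the clause was written with grade 2 in mind. The grade 3 description does not mention intervention as such, so a filter could in principle remove some grade 3 events.

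**Step 4. Are serious events lost?** No. Section 9.3 requires every serious event to be reported to the drug supplier whatever the suspected cause, and Section 9.2.4.2 puts all serious events in the monitoring board's reports. The possible loss concerns non-serious events on the case report form.

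**Step 5. Do the formal rules change?** No.
- The stopping rule in Section 8.5 counts related deaths, Grade IV thrombosis or embolism, and "Any Grade IV toxicity excluding readily reversible metabolic or laboratory abnormalities". Grade 2 events never enter it. A Grade IV hypertension event is above grade 2, and Table 7 describes grade 4 as needing urgent intervention, so it is recorded under every reading.
- The two-stage design in Section 8.3 counts responders only.

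**Step 6. Scale, for illustration only.** The documents give no rate of grade 2 hypertension, so the rate *q* below is an assumption. With n = 25 (Section 8.3), one unrecorded subject is 1/25 = 4 percentage points. If grade 2 events are not recorded, the expected number of affected subjects is 25*q*, and the chance of at least one is 1 − (1 − *q*)^25.

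| Assumed *q* | Expected subjects | Chance of at least one |
|---|---|---|
| 2% | 0.5 | 39.7% |
| 5% | 1.25 | 72.3% |
| 10% | 2.5 | 92.8% |
| 20% | 5 | 99.6% |

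The table shows how the loss would depend on the rate. It does not predict the rate.

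**The case against.** The strongest reply is that the sentence is a drafting slip. Its reasoning is about grade 1, and Table 7 already ties grade 2 to an intervention, so *grade 2 or greater* is a natural reading. On that reading grade 2 events can be recorded as for any other event. This stands as a plausible account of intent, and it limits the point to what follows from the literal words. It does not remove the need for correction, because staff can only apply what is written.

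A second reply is that the sentence is a deliberate exception and that Section 9.2.2 already sets different thresholds for blood counts and laboratory values. The second part is true, so a separate threshold is not a defect in itself. But the blood-count exemption comes with a reason that fits it, and the hypertension rule does not.

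A third reply is that little is at stake. Hypertension is absent from the adverse-event lists in Tables 9 to 13, and Section 4.2.11 excludes uncontrolled hypertension and a history of labile hypertension. This stands too: the documents give no ground for expecting many missed events, and equally no figure showing that there would be none.

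A reader might go further and infer that all grade 2 hypertension is certain to drop out of the primary safety endpoint, or that the hypertension rate is biased and cannot be compared with other events. The documents do not support that. The loss depends on the literal reading, and serious events are reported in any case. A rate openly labelled as grade 3 or higher would be a valid rate for those grades; it misleads only if presented beside grade 2 and higher rates without saying so.

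**Conclusion.** The two sentences in Section 9.2.2 conflict at grade 2, and nothing in the documents justifies the narrower threshold. If the hypertension sentence is applied as written, non-serious grade 2 hypertension is not recorded; if its intervention clause is also treated as a filter, neither is hypertension of grade 3 or higher without intervention. The hypertension line of the 6-month toxicity profile would then be understated relative to the threshold used for other clinical events.

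The size is unknown because no rate is given; the only firm figure is 4 percentage points per subject at n = 25. The effect is confined to descriptive safety reporting. The conclusion assumes that the more specific sentence governs in practice, which the text permits but does not establish. This is a minor point, worth correcting because it touches a primary endpoint and events left off the case report form may be hard to recover later.

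**What to change.** Reconcile the two sentences in Section 9.2.2 to a single recording threshold for hypertension, for example: *hypertension of CTCAE grade 2 or greater will be documented*. In the same edit, either delete the clause on medical intervention or state that it describes the grade and is not an additional condition. Changing the grade wording alone would leave that second ambiguity in place. Align the case report form guidance.

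If a higher threshold is intended, give the reason in Section 9.2.2 and footnote the hypertension row in the safety tables with the threshold used.

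If subjects have already been followed under the present wording, establish which reading was applied and check their source notes for unrecorded events. Section 9.5 makes the medical record the primary source for the database, so this should be feasible where the notes are adequate.

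The cost is a short text change and slightly more adverse-event recording, plus the source check if one is needed. Treatment, sample size and stopping boundaries are not affected.
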